6.3.1 Handling of study treatment and other treatment

6.3.1.1 Handling of study treatment

Study treatment must be received by a designated unblinded person at the study site, handled and stored safely and properly and kept in a secured location to which only the designated site personnel have access. Upon receipt, all study treatment must be stored according to the instructions specified in the Pharmacy Manual.

Clinical supplies are to be dispensed only in accordance with the protocol. Technical complaints are to be reported to the respective Novartis Country Organization Quality Assurance. Please refer to procedures as outlined in the Pharmacy Manual.

Medication labels will be in the local language and comply with the legal requirements of each country. They will include storage conditions for the study treatment but no information about the participant except for the medication number.

The designated unblinded site personnel must maintain an accurate record of the shipment and dispensing of study treatment in a drug accountability log. Monitoring of drug accountability will be performed by monitors during site visits or remotely and at the completion of the trial.

At the conclusion of the study, and as appropriate during the course of the study, the designated site personnel will return a copy of the completed drug accountability log to the Novartis monitor or to the Novartis address provided in the investigator folder at each site.

OAV101 will be stored in a locked, limited access room under the responsibility of the designated unblinded personnel (e.g., pharmacists) in accordance with local regulations, policies, and procedures. Control of storage conditions, especially control of temperature (e.g., refrigerated/freezer storage) and information on in-use stability and instructions for handling prepared OAV101 should be managed in accordance with the Pharmacy Manual.

Any quality issue noticed with the receipt or use of OAV101 (e.g., deficiency in condition, appearance, pertaining to documentation, labeling, expiration date, etc.) should be promptly reported to the Sponsor in accordance with procedures outlined in the Pharmacy Manual.

Under no circumstances will the Investigator supply OAV101 to a third party, allow OAV101 to be used other than as directed by this clinical trial protocol, or dispose of OAV101 in any other manner.

6.3.1.2 Handling of other treatment

The following non-study treatment has to be monitored specifically:

The designated site personnel must maintain an accurate record of the shipment and dispensing of prednisolone/placebo treatment in a drug accountability log. Monitoring of drug accountability will be performed by monitors during site visits or remotely and at the completion of the trial. Participants/caregivers must be instructed to record the dose and date of prophylactic prednisolone/placebo taken/administered at home in the diary provided by Novartis and will be asked to return all unused study treatment and packaging at the end of the study or at the time of study discontinuation.

At the conclusion of the study, and as appropriate during the course of the study, the participant will return all unused prednisolone and matching placebo for accountability and reconciliation, which will be completed by designated site personnel and verified by the Novartis monitor. Upon completion of these tasks, drug can be destroyed at site according to institutional guidelines.

6.4 Participant numbering, treatment assignment, randomization

6.4.1 Participant numbering

Each participant is identified in the study by a Participant Number (Participant No.), that is assigned when the participant is enrolled for screening and is retained for the participant throughout his/her participation in the trial. A new Participant No. will be assigned at every subsequent enrollment if the participant is rescreened. The Participant No. consists of the Site Number (Site No.) (as assigned by Novartis to the investigative site) with a sequential participant number suffixed to it, so that each participant's participation is numbered uniquely across the entire database. Upon signing the informed consent form, the participant is assigned to the next sequential Participant No. available.

The Investigator or designated staff will contact the IRT and provide the requested identifying information to register the participant. Once assigned, the Participant No. must not be reused for any other participant and the Participant No. for that individual must not be changed unless the participant is rescreened. The site should select the eCRF book with a matching Participant Number from the EDC system to enter data. If the participant fails to be treated for any reason, the IRT must be notified within 2 days that the participant was not treated. Rescreening is allowed for participants that were screen failures for a temporary reason. All eligibility criteria must be re-checked and met prior to enrollment of the participant into the study. A new Participant No. should be assigned for all rescreened participants.

[figure not shown]
A new ICF will need to be signed if the investigator chooses to rescreen the participant after a participant has screen failed, and the participant will be assigned a new Participant No.

6.4.2 Treatment assignment, randomization

At Screening Visit 3, all eligible participants will be randomized via Interactive Response Technology (IRT) to one of the treatment arms. The investigator or his/her delegate will contact IRT after confirming that the participant fulfills all inclusion/exclusion criteria. The IRT will assign a randomization number to the participant, which will be used to link the participant to a treatment arm and will specify a unique medication number for the first package of study treatment to be dispensed to the participant.

The randomization numbers will be generated using the following procedure to ensure that treatment assignment is unbiased and concealed from participants and investigator staff. A participant randomization list will be produced by Novartis GCS using a validated system that automates the random assignment of participant numbers to randomization numbers. These randomization numbers are linked to the different treatment arms, which in turn are linked to medication numbers. A separate medication list will be produced by or under the responsibility of Novartis GCS using a validated system that automates the random assignment of medication numbers to packs containing the study treatment.

Randomization will **CCI**

CCI

The randomization scheme for participants will be reviewed and approved by a member of the Randomization Office.

6.4.2.1 Replacement policy

No participant replacement will be done for this study.

6.5 Treatment blinding

With the exception of designated unblinded site and Sponsor personnel, all other personnel, including participants, Investigator staff, clinical evaluators performing the assessments, and sponsor will remain blinded to the identity of the treatment from the time of randomization until database lock.

Treatment Period 1 (Screening/Baseline through Week 52)

Randomization: After eligibility for the trial has been determined and informed consent has been obtained, study participants will be randomly assigned using central randomization in a 3:2 ratio (OAV101: sham procedure). Randomization data will be kept strictly confidential until the time of the primary analyses which will occur once the last participant completes Week 52, and will not be accessible by anyone else involved in the study with the following exceptions of unblinded study staff listed below. At this time, treatment assignments will be unblinded to designated sponsor personnel and a full analysis of all efficacy and safety data will be conducted.

Parents and key study personnel (e.g, outcome assessors) must not be present during the procedure to ensure blinding.

The following personnel will be unblinded to the identity of the treatment from the time of randomization:

- IRT personnel who require access to unblinded data
- For the purpose of DMC support, an independent analysis team (Unblinded Statistician/ Statistical Programmer/ Data Analyst)

Sites:

- Unblinded site pharmacist (or equivalent)
- Designated site physician (e.g., Interventional Radiologist) whose role is to perform the sham procedure (i.e., needle prick) or to administer OAV101.
- Designated Procedure Room staff required during the sham procedure or during OAV101 administration

Sponsor:

- Global Clinical Supply management
- Designated Clinical Research Monitors (CRAs)
- Novartis Scientific Monitor
- Unblinded Medical Monitor
- Other designated personnel

Treatment and Follow-up Period 1 blinding

Blinding of Treatment Allocation: The identity of ancillary study treatment (prednisolone and matching placebo) will be concealed by identical packaging, labeling, schedule of administration and appearance.

Unblinding may occur in the event of participant emergencies. The Principal Investigator and Novartis will assess whether the participant whose treatment code has been broken should be withdrawn from the study prematurely (e.g., will not proceed into Treatment Period 2).

If a participant has been randomized to OAV101 administration, the unblinded pharmacist (or equivalent) will prepare a single intrathecal dose of OAV101. The prepared dose will be delivered to the location of the procedure. Participants will be adequately sedated (following institutional guidelines) for lumbar puncture to avoid any awareness of the procedure. A qualified interventional radiologist or specialist (e.g., neurologist) who is unblinded to study treatment will perform the intrathecal administration of OAV101 or the sham procedure. Any study personnel involved with patient treatment or evaluation (e.g., Principal Investigator, study coordinator, site clinical evaluator) cannot be present at the time of the procedure. Parents/caregivers must not be present in the procedure room. Treatment assignment will remain blinded to all patients, site and Novartis personnel (unless otherwise specified), and will similarly be blinded to post-treatment anti-AAV9 antibody results. The pharmacist (or equivalent) and the clinician administering the procedure will be specifically instructed not to discuss any details regarding patient dosing with members of the study team (including the Principal Investigator, study coordinator, and site clinical evaluator) involved in the care or evaluation of the patients.

Prednisolone and placebo prednisolone administration and blinding: Prednisolone administration is required at the time of OAV101 dosing to suppress the immune response. For those participants receiving OAV101, prednisolone will be given **CCI**
[REDACTED]
[REDACTED]

[REDACTED] In order to mimic the prednisolone prophylaxis in the OAV101 treatment group and preserve blinding, the sham procedure group will receive a placebo formulation that is identical in packaging, labeling, schedule of administration, taste, and odor.

Post-administration follow-up and blinding: The Principal Investigator, physical therapists and any other clinical evaluators will be blinded at all times. In order to limit any potential bias, the HFMSE and RULM assessors (i.e., physical therapists or equivalent) should not have access to any study-related data, other than the data for the assessment(s) which they will administer. Unblinded site personnel will be responsible for performing the OAV101 dosing/sham procedure and may also assess subject safety and AEs within the 2 to 3 days following the study

treatment administration (i.e., during the in-hospitalization period). The unblinded personnel must not be involved in any other aspect of the study, other than the responsibilities detailed in the Pharmacy Manual, and must not divulge the subject's treatment assignment. The blinded personnel will be responsible for all other aspects of the study.

Treatment and Follow-up Period 2 blinding

Anti-AAV9 antibody results **CCI** will be supplied to designated unblinded Novartis personnel. Designated unblinded Novartis personnel will communicate to the investigator when a participant (who received sham procedure in Period 1) has an anti-AAV9 antibody titer reported as elevated (reference to $> 1:50$ or a validated result consistent with being elevated) ([Table 6-4](#)). Novartis GCS will issue OAV101 only if anti-AAV9 antibody titer is not reported as elevated.

At the Week 52 + 1 Day visit, all eligible participants who received the sham procedure in Treatment Period 1 (Day 1) will receive a lumbar puncture and the administration of OAV101 1.2 and all eligible participants who received OAV101 in Period 1 will receive the sham procedure. Blinding will be maintained in the same manner described above for Treatment Period 1. Participants will be followed until Week 64 for efficacy and safety. A small number of control patients (estimated as ≤ 5) may not receive OAV101 treatment at Week 52 due to elevated AAV9 antibodies and would be unblinded. Sham-procedure participants who do not continue to Treatment Period 2 will be captured on the eCRF disposition page.

The DMC responsible for assessments on the safety and overall risk to benefit ratio of the study conduct will have access to the results with aggregated treatment assignment ([Section 10.4.1](#)). An independent team of statisticians and programmers, not otherwise involved in the conduct of the study, will be responsible for the timely coordination and delivery of the data to the DMC on a regular basis and will have access to the aggregated treatment assignment and patient level data as requested.

Table 6-4 Blinding and unblinding plan

Role	Time or Event		
	Randomization list generated	Treatment allocation & dosing	Safety event (single subject unblinded)
Participants	B	B	UI
Site staff	B	B	UI
Unblinded site staff (see text for details)	B	UI	UI
Drug Supply and Randomization Office	UI	UI	UI
Unblinded sponsor staff (see text for details)	B	UI	UI
Statistician/statistical programmer/data analysts	B	B	UI
Independent committees used for assessing interim results	B	UI	UI
All other sponsor staff not identified above	B	B	UI
B Remains blinded			
UI Allowed to be unblinded on individual patient level			

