----------------	---

	
Natural history assessment of late onset SMA patients demonstrates CCI
 
CC1 rationale: CCI

Participant and investigator blinding	Blinding of participants, physical/occupational therapist (or national equivalent) who performs HFMSE and RULM, and the investigator controls for bias during study endpoint assessment.
Duration of study	A clinical study duration of 52 weeks optimizes the probability of clearly demonstrating the potential clinical efficacy of OAV101 for IT administration while limiting the time SMA participants randomized to the sham procedure arm are required to remain on a non-active-treatment regimen. The data for assessment of endpoints is based on a 52-week follow-up period.
Sham procedure comparator	The use of a sham procedure as a comparator will provide a comparison group for an unbiased collection and assessment of efficacy, safety and tolerability. The sham procedure will consist of a small needle prick on the lower back at the location where the lumbar puncture injection is normally made. The needle will break the skin but no needle insertion for lumbar puncture will occur. Lumbar puncture and OAV101 administration should be performed using an atraumatic spinal needle (e.g., Whitacre, 22 or 25 gauge) which significantly lowers the incidence of blood patch treatment (Hatfield et al 2008).
Observation period	Review of data from the previous AVXS-101-CL-102 study confirmed the importance of following participants for 52 weeks to evaluate the statistical significance and clinical meaningfulness of the observed changes. Data analysis at time points before 52 weeks may not have sufficient power to adequately evaluate therapeutic efficacy. Although blinding is maintained at 52 weeks when a second blinded OAV101 treatment of control patients and sham procedure with needle prick is performed on treated participants, the data for assessment of endpoints is based on a 52-week follow-up period.

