The sham procedure will be performed in an ICU patient room or other appropriate setting (e.g., interventional suite, operating room, dedicated procedure room) with immediate access to acute critical care management. Parents/caregivers must not be present during the procedure to ensure blinding (See [Section 6.5](#)). The sham procedure will consist of a small needle prick on the lower back at the location where the LP injection is normally made. The needle will break the skin, but no needle insertion for lumbar puncture will occur. **CCI**

[REDACTED] A detailed description of the sham procedure is provided in the Pharmacy Manual.

Post administration procedures

Following administration of gene replacement therapy/sham procedure, participants should return to an appropriate designated setting to ensure close monitoring of vital signs and AEs. Vital signs will be monitored as described under Vital Signs ([Section 8.4.4](#)). Participants should be maintained in an appropriate inpatient setting for 24 to 48 hours after the start of gene replacement therapy/sham procedure.

Participants will be kept in the ICU patient room or other appropriate setting (e.g., interventional suite, operating room, dedicated procedure room) with immediate access to acute critical care management for 24 to 48 hours for closer monitoring of mental status. During the inpatient stay, personnel are required to follow appropriate safety precautions as per institutional standards for infection control; standards may require personal protective equipment such as gowns, gloves, masks, glasses, and closed-toe shoes. Participants may be discharged from the hospital when the following criteria are met:

- Afebrile
- Absence of hypersensitivity reactions
- Absence of meningism
- Absence of abnormal laboratory values suggestive of possible CNS infection or complication

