10.1 Definition of adverse events and reporting requirements

10.1.1 Adverse events

An adverse event is any untoward medical occurrence (e.g., any unfavorable and unintended sign [including abnormal laboratory findings], symptom or disease) in a clinical investigation participant after providing written informed consent for participation in the study. Therefore, an AE may or may not be temporally or causally associated with the use of a medicinal (investigational) product. A treatment-emergent adverse event is defined as any event not present prior to the initiation of the treatment or any event already present that worsens in either intensity or frequency following exposure to the treatment.

The Investigator has the responsibility for managing the safety of individual participant and identifying adverse events.

Novartis qualified medical personnel will be readily available to advise on trial related medical questions or problems.

The occurrence of AEs must be sought by non-directive questioning of the participant at each visit during the study. Adverse events also may be detected when they are volunteered by the participant during or between visits or through physical examination findings, laboratory test findings, or other assessments.

Adverse events must be recorded under the signs, symptoms, or diagnosis associated with them, accompanied by the following information (as far as possible) (if the event is serious refer to [Section 10.1.2](#)):

Adverse events will be assessed as follows:

1. Severity grade
 - mild: usually transient in nature and generally not interfering with normal activities
 - moderate: sufficiently discomforting to interfere with normal activities
 - severe: prevents normal activities
2. Its relationship to the study treatment. If the event is due to lack of efficacy or progression of underlying illness (i.e., progression of the study indication) the assessment of causality will usually be 'Not suspected.' The rationale for this guidance is that the symptoms of a lack of efficacy or progression of underlying illness are not caused by the trial drug, they happen in spite of its administration and/or both lack of efficacy and progression of underlying disease can only be evaluated meaningfully by an analysis of cohorts, not on a single participant
3. Its duration (start and end dates or ongoing)

4. Whether it constitutes an SAE (see [Section 10.1.2](#) for definition of SAE) and which seriousness criteria have been met

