2.7.1 Adverse events (AEs)

An overview summary table of AEs reported through the end of Follow-up Period 1 will be presented by Treatment Period 1 treatment group (OAV101, sham), consisting of the number and percentage of participants experiencing at least one event for each of the following categories:

- Any TEAE
- Any TEAE related to study treatment
- Any serious TEAE
- Any serious TEAE related to study treatment
- Any severe TEAE
- Any TEAE leading to discontinuation from study
- Any TEAE leading to death
- Any AESI (refer to [Section 2.7.1.1](#) of this SAP)

The number and percentage of participants with TEAEs will be summarized in the following ways:

- by treatment group, primary SOC, and PT along with the total number of events
- by treatment group, primary SOC, PT, and maximum severity

Separate summaries by Treatment Period 1 treatment group (OAV101, sham), primary SOC, and PT will be provided for TEAEs leading to death, TEAEs related to study treatment, TEAEs related to prednisolone/placebo, serious TEAEs, serious TEAEs related to study treatment, TEAEs leading to discontinuation from study, non-serious TEAEs reported in >5% of participants, and AESIs.

Additionally, separate summaries by Treatment Period 1 treatment group (OAV101, sham) and PT will be provided for TEAEs, TEAEs related to study treatment and serious TEAEs.

All information obtained on AEs through the end of study will be listed by Treatment Period 1 treatment group (OAV101, sham) and participant.

The number and percentage of participants with TEAEs reported within 72 hours of treatment with the study treatment will be summarized by treatment group, primary SOC and PT.

A similar, second set of outputs will be produced to summarize the TEAEs reported after dosing with OAV101 and through the end of Follow-up Period 2 using OAS. In this second set of outputs, only TEAEs reported on/after OAV101 dosing (during Treatment Period 1 and through the end of study for participants originally randomized to OAV101, during Treatment Period 2 and through the end of study for participants originally randomized to sham administration) will be considered.

For the legal requirements of ClinicalTrials.gov and EudraCT, two required tables on TEAEs which are not serious adverse events with an incidence > 5% and on treatment emergent serious

adverse events and SAE suspected to be related to study treatment will be provided by system organ class and preferred term based on the SAF.

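### Adverse events in the first days after the procedure are not assured to be rated blind, because staff who know the treatment are permitted to assess them

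*Protocol*

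**What the plan says.** Protocol 6.5 lists the site pharmacist, the physician who doses or performs the sham, and the procedure room staff as unblinded. It then says that unblinded site personnel "may also assess subject safety and AEs within the 2 to 3 days following the study" treatment, and limits this to the hospital stay: "treatment administration (i.e., during the in-hospitalization period". Apart from that and the duties set out in the Pharmacy Manual, these staff are to have no part in the study, and blinded staff do the rest.

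Other passages promise more. The introduction to Protocol Section 6 says that blinding is strict from the time the child is out of the procedure room. Section 6.5 itself says "The Principal Investigator, physical therapists and any other clinical evaluators will be blinded at all times". Table 4-1 in Section 4.1 gives as the design rationale that blinding of participants, motor assessors "and the investigator controls for bias during study endpoint assessment".

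Protocol 10.1.1 sets out what assessing an adverse event involves: a severity grade, "Its relationship to the study treatment", and whether the event is serious, among other items. It makes the investigator responsible for identifying events but does not name who makes each rating. On the length of stay, Protocol 6.3 says: "Participants should be maintained in an appropriate inpatient setting for 24 to 48 hours after the start of gene replacement therapy/sham procedure".

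SAP 2.7.1 plans that "TEAEs reported within 72 hours of treatment with the study treatment will be summarized by treatment group", system organ class and preferred term. It also tabulates by arm, through Follow-up Period 1, items such as "Any TEAE related to study treatment" and TEAEs by maximum severity.

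**The concern.** The people given this permission know whether the child had a lumbar puncture with vector or only a skin prick. Severity, seriousness and causality are judgements, and knowing the procedure can shift them. It can also affect how closely a child is watched. Under Protocol 6.1 the term study treatment includes the sham, so relatedness ought to be judged on the same footing in both arms. A rater who knows that a child had only a prick may find that hard to do.

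At stake is the acute tolerability comparison. Protocol 4.5.3 lists headache and back pain among the risks of lumbar puncture, and the sham involves no lumbar puncture, so a real difference between arms is plausible. If unblinded staff rated some of these events and nobody recorded which, a real procedural effect could not be told apart from an effect of knowing the assignment. The results would still be presented as coming from a double-blind study.

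**Working it through.** The plan gives no figure on this point. The check is a comparison of passages, followed by a calculation of how far the windows overlap.

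**1. Is rating inside the permission?** Section 6.5 uses the verb assess for what unblinded staff may do with adverse events. Section 10.1.1 uses the same verb to introduce severity, relationship and seriousness. Section 6.5 gives blinded staff everything else, so early assessment lies inside the exception. The rule that unblinded staff take no further part is then no safeguard here. Section 10.1.1 assigns identification of events to the investigator, and Section 10.2 has the investigator certify the data. Neither assigns the rating of in-hospital events to a blinded person. Table 6-4 shows who is blinded at which stage and does not settle the question.

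**2. How much of the 72-hour window is exposed?** Overlap = exposed hours / 72.

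| Source | Hours | Share of 72 h |
|---|---|---|
| Protocol 6.3, stay of 24 to 48 h | 24 to 48 | 24/72 = 33% to 48/72 = 67% |
| Protocol 6.5, 2 to 3 days | 48 to 72 | 48/72 = 67% to 72/72 = 100% |

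The two statements agree only at 48 hours. Section 3 plans hospitalization on Day 1, Day 2 and an optional Day 3. If Section 6.5 is counting those calendar days, the shorter range applies. The text does not say so.

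**3. Which outputs are touched?**
- The 72-hour summary is by system organ class and preferred term. It carries no severity or relatedness, so only ascertainment matters there.
- Severity and relatedness enter through the tables that run to the end of Follow-up Period 1. Early events are only some of the events in them.
- No output separates events by who assessed them, and neither document says that the assessor's blind status is recorded.
- HFMSE and RULM are scored by therapists who stay blinded and have no part in this.

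**4. Can the bias be sized?** No. The documents give no early TEAE rate and no measure of differential recording. As a pure assumption, take the same true rate p in both arms and d percentage points of over-recording under OAV101. The apparent risk ratio is (p + d)/p. For p from 20% to 40% and d from 5 to 20 points, it runs from 45/40 = 1.13 to 40/20 = 2.0, and with d = 0 it is 1. The result simply returns the value chosen for d, so it shows what kind of distortion is possible and estimates nothing.

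**The case against.** The strongest reply is that Section 6.5 only permits early assessment by unblinded staff. The principal investigator stays blinded and investigators are responsible for identifying events, so a blinded person may in practice rate every one. Parents are kept out of the room, children are sedated, and events are sought by non-directive questioning, so many complaints will come from people who do not know the assignment. Vital-sign schedules, pre-discharge hematology and discharge criteria are the same in both arms. The 72-hour summary is descriptive. Over-recording under OAV101 would also make the product look less safe, not more. The Pharmacy Manual, which Section 6.5 cites for the duties of unblinded staff, was not available and may narrow their role.

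Much of this stands. A reader might infer that the early comparison is unblinded as a matter of fact, or that the whole 72-hour table and every early relatedness rating are affected. The documents do not support that: the wording is permissive, the rater is not named, and the stated stay is shorter than 72 hours. Nor does the sentence about clinical evaluators make a clean contradiction, because Section 8.3.1 uses that term for the therapists who score the motor scales.

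None of this supplies the missing safeguard. Responsibility for identifying events and certifying data does not say who judges severity and cause. The direction of any bias is a reasonable expectation that the documents do not establish.

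**Conclusion.** The point holds in a limited form. The plan allows staff who know the procedure to assess in-hospital adverse events and does not require a blinded rating of them. That sits in tension with the introduction to Section 6 and with the reliance on investigator blinding in Table 4-1. Early ascertainment and relatedness are therefore not assured to be blinded.

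The exposure is 33% to 67% of the 72-hour window on the stated stay, or 67% to 100% on the 2 to 3 day wording, together with the early events in the severity and related-TEAE tables. This rests on reading assess in Section 6.5 in the sense of Section 10.1.1, and on no further restriction in the Pharmacy Manual. How often unblinded staff actually rated events is unknown. A quoted risk ratio such as 1.5 would be tempting, but it depends entirely on assumed rates and should not be presented as a finding. The efficacy conclusions are not in question.

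**What to change.** **Protocol 6.5.** Leave bedside observation and acute care by unblinded staff as they are. State that severity, seriousness and causality of every adverse event, including in-hospital events, are rated by the blinded investigator from the recorded facts and without knowledge of the procedure. Record whether unblinded staff first observed or rated the event. Reconcile the Section 6 introduction with Sections 6.3, 6.5 and 10.1.1 on the length of the window and on who rates, and check the Pharmacy Manual against them.

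**SAP 2.7.1.** Base the severity and related-TEAE tables on the blinded rating. Flag and footnote early events assessed by unblinded staff, including events already collected where records permit. Do not exclude them: that would remove real events, in proportions that depend on site staffing.

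**Cost.** A paragraph in the protocol, one eCRF item, a flag and a footnote, with no extra staff. The blinded rating would be entered after a short delay. SAP Section 4 says that the study is fully enrolled, so the protocol and eCRF changes can do little for Period 1. For those data the practical remedy is to establish from site records who assessed the in-hospital events and, where that cannot be done, to say in the footnote that assessment may have been unblinded. Section 6.5 applies the same blinding arrangements in Period 2, so the change would also cover any second procedures still to come.
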